Potential patient-subjects will be identified by neurosurgeons on the treatment team. Patients will be recruited and screened for participation in the drug vs placebo or observational cohort by a member of the research team prior to discharge. Patient inclusion and exclusion will be determined by the medical record as well as in-person by the provider. The Montreal Cognitive Assessment will be administered prior to the consent to determine baseline cognitive state. We will also conduct screening to determine if the patient is currently receiving therapy for depression or related mental health diagnoses. Any recruiter who administers the MoCA completes MoCA training and certification. Patients scoring >20 on the MoCA are considered of appropriate cognitive function to participate in the study.

Patients recruited for the drug vs placebo cohort will be provided with a detailed explanation regarding the study protocol, occurrence of depression in aneurysmal subarachnoid hemorrhage and the potential treatment effects of fluoxetine. Patients will have an opportunity for questions before providing before consent. Decisional capacity will be determined by having participants confirm their understanding of the study purpose and procedure, and the risks, benefits and alternatives to participating in the study.

Interventions

Explanation for the choice of comparators

If a patient chooses to decline treatment with fluoxetine but is eligible for the observational cohort, they will be given the necessary study information. Patients can choose to provide consent anytime between approach and discharge. Patients may revoke their informed consent at any time by contacting the research team.

Intervention description

Patients deemed eligible for inclusion in the drugs vs. placebo or observational cohort will be approached for consent in the inpatient ward as they are nearing discharge after aSAH. After consent is obtained, patients will be randomized to either a placebo or fluoxetine-treatment group. Patients that decline participation in the drug vs placebo arm may be enrolled in the observational cohort.

For patients participating in the drug vs. placebo cohort, the study drug will be provided at no cost for the duration of the trial (1 year).

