Sequence generation

Simple randomization schemes will be utilized for the drug cohort and placebo cohort. For each cohort, subjects will be randomized in a 1 to 1 ratio to receive either the SSRI antidepressant or placebo drugs. Randomization will be done after the participant or

LAR as signed the ICF. Randomization will be performed by the study pharmacist. Study team, study assessor, study investigator is blinded until the subject exits the study, need to unblind for medical intervention, or end of the study.

Assignment of interventions: Blinding

Who will be blinded

Trial participants, care providers, outcome assessors will stay blinded. Placebo vs study drug will be prepared and dispensed by local study pharmacist. Only the study pharmacy will know the designation of each participant until the clinical team request the information for health care purposes or when the participants exit the study.

Procedure for unblinding if needed

If an adverse event occurs in which the disclosure of the treatment arm is necessary for medical treatment, the disclosure will be provided to the patient and/or provider.

Data collection and management

Plans for assessment and collection of outcomes

Preventative treatment of poststroke depression in aneurysmal subarachnoid hemorrhage					
Activity	Initial Screening	Baseline	6-week	6-month	12-month
Eligibility Screen	x				
Montreal Cognitive Assessment (MoCA)*	x				
Enrollment	x				
Consent	x				
OnCore/EPIC Update	x	x	x	x	x
Pharmacy Prescription Fluoxetine (every 90 days)		x	x	x	
Patient Health Questionnaire (PHQ-9)		x	x	x	x

Hamilton Rating Scale for Depression (HAM-D)**		x	x	x	x
36-Item Short Form Survey (SF-36)		x	x	x	x
Barthel Index		x	x	x	x
Hamilton Anxiety Rating Scale (HAM-A)		x	x	x	x
Multidimensional Scale of Perceived Social Support		x	x	x	x
Sleep Disturbance (PROMIS)		x	x	x	x
Self Report Health Service Utilization and Medication Use		x	x	x	x
Fatigue Severity Scale (FSS)		x	x	x	x
Disclosure of Interventional Cohort					x
*MoCA score must score more than 20 in order to be enrolled and consented into the study					
**HAM-D only conducted when pt scores greater than 4 on PHQ-9					

Confidentiality and Data management

All research data will be deidentified. A single-master key will be retained. All data will be stored on a secure research database or in a secure cabinet on a secure floor.

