An independent medical monitor, an appropriately qualified physician with no conflict of interest and meeting the NINDS recommendation of being otherwise unaffiliated with the study or an institution conducting the study, will perform safety-focused reviews considering adverse events at a minimum of 6 month intervals.

Adverse event reporting and harms

The PI (or approved co-investigator) will monitor the study with prompt reporting of adverse events and other study related information to the IRB and other agencies as

appropriate. Non-serious adverse events and unrelated serious adverse events will be reported in the annual progress report. Serious adverse events that could be related to the study should be reported within 7 days of becoming aware of the event. At any time, if a patient presents suicidal ideations, the patient will be immediately referred to psychiatric service for further evaluation and the event reported.

If an adverse event occurs in which the disclosure of the treatment arm is necessary for medical treatment, the disclosure will be provided to the patient and/or provider.

Frequency and plans for auditing trial conduct

Internal audit will be conducted routinely with study PI and the study team. An independent medical monitor, an appropriately qualified physician with no conflict of interest and meeting the NINDS recommendation of being otherwise unaffiliated with the study or an institution conducting the study, will perform safety-focused reviews considering adverse events at a minimum of 6 month intervals.

Plans for communicating important protocol amendments to relevant parties (e.g. trial participants, ethical committees)

Team meetings by the PI and staff will be conducted on a routine basis to discuss any new adverse events or changes in the protocol. This plan will be revised and updated if the benefit-risk analysis changes.

Dissemination plans

A description of this clinical trial will be available on <https://clinicaltrials.gov>, as required by U.S. Law. This Web site will not include information that can identify you. At most, the Web site will include a summary of the results. You can search this Web site at any time.

Patient Health Questionnaire Depression (PHQ-9) (Kroenke et al., 2001)

For this next section, the questions I'll be asking you will be in regards to your mood in the past month, since your injury.

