Phq	Since your injury, how often have you been bothered by any of the following problems?	Not at all	A little of the time	More than half the time	Nearly all the time
1.	Little interest or pleasure in doing things	0	1	2	3
2.	Feeling down, depressed or hopeless	0	1	2	3
3.	Trouble falling or staying asleep, or sleeping too much	0	1	2	3
4.	Feeling tired or having little energy	0	1	2	3
5.	Poor appetite or overeating	0	1	2	3
6.	Feeling bad about yourself- or that you are a failure or have let yourself or your family down	0	1	2	3
7.	Trouble concentrating on things, such as reading the newspaper or watching television	0	1	2	3
8.	Moving or speaking so slowly that other people could have noticed? Or the opposite - being so fidgety or restless that you have been moving around a lot more than usual	0	1	2	3
9.	Thoughts that you would be better off dead or of hurting yourself in some way. *Note, if any endorsement, RA assess further and contact PI [9a.] Do you currently have plans to harm yourself or take your own life? Yes No if no, proceed to next section [9b.] Have you attempted to carry out this plan in the past two weeks? Yes No	0	1	2	3
10.	[If YES to any problems] How difficult have these problems made it for you to do your work, take care of things at home, or get along with other people?	0 Not at all	1 A little bit	2 Moderately	3 Extremely

Total Score: _____

The Hamilton Rating Scale for Depression

1. DEPRESSED MOOD (Sadness, hopeless, helpless, worthless)

- 0=** Absent
- 1=** These feeling states indicated only on questioning
- 2=** These feeling states spontaneously reported verbally
- 3=** Communicates feeling states non-verbally—i.e., through facial expression, posture, voice, and tendency to weep
- 4=** Patient reports VIRTUALLY ONLY these feeling states in his spontaneous verbal and non-verbal communication

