22. During the **past 4 weeks**, how much did **pain** interfere with your normal work (including both work outside the home and housework)?

- 1=** Not at all
- 2=** A little bit
- 3=** Moderately
- 4=** Quite a bit
- 5=** Extremely

These questions are about how you feel and how things have been with you **during the past 4 weeks**. For each question, please give the one answer that comes closest to the way you have been feeling.

How much of the time during the **past 4 weeks**...

	All of the time	Most of the time	A good bit of the time	Some of the time	A little of the time	None of the time
23. Did you feel full of pep?	1	2	3	4	5	6
24. Have you been a very nervous person?	1	2	3	4	5	6
25. Have you felt so down in the dumps that nothing could cheer you up?	1	2	3	4	5	6
26. Have you felt calm and peaceful?	1	2	3	4	5	6
27. Did you have a lot of energy?	1	2	3	4	5	6
28. Have you felt downhearted and blue?	1	2	3	4	5	6
29. Did you feel worn out?	1	2	3	4	5	6
30. Have you been a happy person?	1	2	3	4	5	6
31. Did you feel tired?	1	2	3	4	5	6

32. During the **past 4 weeks**, how much of the time has **your physical health or emotional problems** interfered with your social activities (like visiting with friends, relatives, etc.)?

- 1=** All of the time
- 2=** Most of the time
- 3=** Some of the time
- 4=** A little of the time
- 5=** None of the time

How TRUE or FALSE is **each** of the following statements for you.

	Definitely true	Mostly true	Don't know	Mostly false	Definitely false
33. I seem to get sick a little easier than other people	1	2	3	4	5
34. I am as healthy as anybody I know	1	2	3	4	5
35. I expect my health to get worse	1	2	3	4	5
36. My health is excellent	1	2	3	4	5

The Barthel Index

FEEDING

0= unable

5= needs help cutting, spreading butter, etc., or requires modified diet

10= independent

BATHING

0= dependent

5= independent (or in shower)

GROOMING

0= needs to help with personal care

5= independent face/hair/teeth/shaving (implements provided)

DRESSING

0= dependent

5= needs help but can do about half unaided

10= independent (including buttons, zips, laces, etc.)

BOWELS

0= incontinent (or needs to be given enemas)

5= occasional accident

10= continent

BLADDER

0= incontinent, or catheterized and unable to manage alone

5= occasional accident

10= continent

TOILET USE

0= dependent

5= needs some help, but can do something alone

10= independent (on and off, dressing, wiping)

TRANSFERS (BED TO CHAIR AND BACK)

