Multidimensional Scale of Perceived Social Support (Zimet, Dahlem, Zimet & Farley, 1988)

	Very strongly disagree	Strongly disagree	Mildly disagree	Neutral	Mildly agree	Strongly agree	Very strongly agree	
1. There is a special person who is around when I am in need.	1	2	3	4	5	6	7	SO
2. There is a special person with whom I can share my joys and sorrows.	1	2	3	4	5	6	7	SO
3. My family really tries to help me.	1	2	3	4	5	6	7	Fam
4. I get the emotional help and support I need from my family.	1	2	3	4	5	6	7	Fam
5. I have a special person who is a real source of comfort to me.	1	2	3	4	5	6	7	SO
6. My friends really try to help me.	1	2	3	4	5	6	7	Fri
7. I can count on my friends when things go wrong.	1	2	3	4	5	6	7	Fri
8. I can talk about my problems with my family.	1	2	3	4	5	6	7	Fam
9. I have friends with whom I can share my joys and sorrows.	1	2	3	4	5	6	7	Fri
10. There is a special person in my life who cares about my feelings.	1	2	3	4	5	6	7	SO
11. My family is willing to help me make decisions.	1	2	3	4	5	6	7	Fam
12. I can talk about my problems with my friends.	1	2	3	4	5	6	7	Fri

The items tended to divide into factor groups relating to the source of the social support, namely family (Fam), friends (Fri) or significant other (SO)

Total Score: _____

LEVEL 2—Sleep Disturbance—Adult*

*PROMIS—Sleep Disturbance—Short Form

If the measure is being completed by an informant, what is your relationship with the individual receiving care?

In a typical week, approximately how much time do you spend with the individual receiving care? _____ hours/week

In the past SEVEN (7) DAYS....					
	Not at all	A little bit	Somewhat	Quite a bit	Very much
1. My sleep was restless.	1	2	3	4	5
2. I was satisfied with my sleep.	5	4	3	2	1
3. My sleep was refreshing.	5	4	3	2	1
4. I had difficulty falling asleep.	1	2	3	4	5
In the past SEVEN (7) DAYS....					
	Never	Rarely	Sometimes	Often	Always
5. I had trouble staying asleep.	1	2	3	4	5
6. I had trouble sleeping.	1	2	3	4	5
7. I got enough sleep.	5	4	3	2	1
In the past SEVEN (7) DAYS....					
	Very Poor	Poor	Fair	Good	Very good
8. My sleep quality was...	5	4	3	2	1

Total/Partial Raw Score: _____

Prorated Total Raw Score: _____

T-Score: _____

Self-Report Health Service Utilization and Medication Use

INTERVIEWER: Did the patient respond to these questions at a previous interview?

If Yes, **SKIP to section 3**. If No, continue

Lifetime utilization questions should only be asked once during the 12 month follow-up period.

 Yes (1) No (0)

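### The PHQ-9 form prints two recall windows that diverge after the first month, so its totals cannot be assured to measure current state or to be comparable across visits

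*Combined protocol and SAP*

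**What the plan says.** The PHQ-9 form appended to the protocol opens with a spoken lead-in saying that the questions are "in regards to your mood in the past month, since your injury". The stem above the scored items then asks "Since your injury, how often have you been bothered by any of the following problems", with no mention of a month. A follow-up to item 9 uses a third period, "Have you attempted to carry out this plan in the past two weeks", but it is an unscored yes/no question and does not enter the total.

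The visit schedule (Plans for assessment and collection of outcomes) places the PHQ-9 at baseline, 6 weeks, 6 months and 12 months. The Participant timeline allows a late visit up to 18 months. Only one version of the form is printed.

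Statistical methods for primary and secondary outcomes plans to report how frequent and how severe the outcomes are at each time point, to analyse the primary outcome at one year, and to use the intermediate visits to describe the course over time.

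The schedule footnote adds "HAM-D only conducted when pt scores greater than 4 on PHQ-9", and the Outcome Measures list agrees in substance. The Intervention description, however, states that every measure is taken at every time point.

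**The concern.** A PHQ-9 item is scored by how much of the time the symptom was present: not at all, a little, more than half, or nearly all. The recall window is therefore the denominator of the score. If the denominator is one month for one patient or visit and the whole time since the haemorrhage for another, the same symptoms can give different totals.

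Read literally, the stem has three effects. The window lengthens at every visit, so later scores overlap the periods already covered by earlier ones. It takes in inpatient days before study drug, since patients are "approached for consent in the inpatient ward as they are nearing discharge after aSAH" and randomised after that. And an item that was ever present can never go back to zero, so the total cannot fall below the number of items ever present. That describes an accumulated history, whereas the analysis section needs the state at each visit and its change over time.

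**Working it through.** The plan gives no figure for this point, so there is none to reproduce. The check sets the two wordings against the visit schedule and then scores two simple patterns.

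**Step 1. How far the windows diverge.** Inputs: one month taken as 30.4 days; visits at 6 weeks, 6 months and 12 months, with a late visit up to 18 months. Share = one month / time elapsed since discharge.

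- 6 weeks: 30.4/42 = 72%
- 6 months: 1/6 = 17%
- 12 months: 1/12 = 8%
- 18 months: 1/18 = 6%

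Counting from discharge understates the gap, because the injury came before it. The documents give no length of stay. Assuming 2 to 4 weeks, the shares become 54% to 43% at 6 weeks (30.4/56 and 30.4/70), about 15% at 6 months, 8% at 12 months and 5% at 18 months. The windows differ at every scheduled follow-up, by about 12-fold at one year.

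**Step 2. What this could do to a score (illustration only).** Assume that patients answer as literal shares of the window: none = 0; above 0 up to 50% = 1; above 50% up to a cut-off c = 2; c or more = 3. At 12 months:

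- Nine items nearly all the time, in the last month only. Past month: 9 × 3 = 27. Since injury: the share is 8%, so 9 × 1 = 9.
- Five items confined to the first 6 weeks after discharge, then resolved. Past month: 0. Since injury: 1.38/12 = 12%, so 5 × 1 = 5.

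These totals are the same for every c from 0.60 to 0.95 and for stays of 0, 2, 3 or 4 weeks, because 8% and 12% lie far below one half. That stability does not test the assumption of literal answering.

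At 6 weeks no score difference can be claimed. Counting from discharge, four items present nearly all the time in the last month only total 12 under the past month. Under the stem the share is 72%, which gives 4 × 3 = 12 if c is 0.70 or less and 4 × 2 = 8 if c is 0.75 or more.

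**Step 3. The link to HAM-D.** If HAM-D is given only above a PHQ-9 of 4, the second pattern (0 against 5) would lead to HAM-D only under the stem. In the first pattern (27 against 9) HAM-D is given either way. If the Intervention description governs and every measure is always taken, this step falls away and Steps 1 and 2 remain. The HAM-D form prints neither of the disputed phrases, so its items and scoring are untouched in both cases.

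**Step 4. How other forms handle recall.** Blocks of the SF-36 ask "how things have been with you during the past 4 weeks", and the PROMIS sleep form uses "In the past SEVEN (7) DAYS". The service-utilisation form is adapted to repeat visits by counting from the previous study interview. The PHQ-9 form has no comparable adaptation.

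**The case against.** The best defence is that the form is read aloud. The lead-in introduces the whole section and names a month, so an interviewer may treat the stem as shorthand for it. This is a reasonable reading and may be what happens in practice. But the stem is the wording attached to the scored items, and nothing in the documents tells interviewers to use the month.

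It can also be said that the score examples are extreme and that their frequency is unknown. That stands: they show what the wording permits, not what it will produce. Symptoms with a steady frequency since the injury would score the same under both windows.

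Three further objections stand as limits. The HAM-D consequence depends on a threshold that the protocol contradicts elsewhere. No general rule for when that threshold would switch follows from these examples, because the result depends on how often each item is present now and earlier. And the SF-36 is not a form with one fixed window: item 2 compares with a year ago and items 3 to 12 ask about the present, so the contrast with other forms is only partial.

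A reader might infer that the treatment comparison is biased. The documents do not support this. Both arms receive the same form, and "Trial participants, care providers, outcome assessors will stay blinded". A reader might also infer that interviewers do apply different windows, or that HAM-D scores themselves lose comparability. The documents show neither.

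**Conclusion.** The inconsistency is on the page and unresolved. PHQ-9 totals cannot be assured to measure current state or to be comparable across visits, and the planned description of depression over time needs both. The divergence in window length is firm: about 12-fold at the one-year visit. Its effect on scores is not quantifiable from the documents, since the 27 against 9 and 0 against 5 examples rest on literal share-of-time answers and on constructed patterns.

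The effect on HAM-D is conditional and limited to who receives it. The point is one of measurement error and an unclear longitudinal measure, not a demonstrated bias between arms. It merits correction because the remedy is cheap.

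**What to change.** Print one recall window in both the lead-in and the stem, the same at all visits. One option is the past month, or the time since the haemorrhage if that is shorter. This keeps mood before the haemorrhage out of the baseline, although a baseline taken near discharge may then still cover less than a month. Brief interviewers on the chosen window. If history since the haemorrhage is wanted, ask it as a separate unscored question.

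Record which wording each score was collected under and describe results by version. With about 20 patients expected (Sample size), any analysis that drops old-wording scores should be supplementary only. Reconcile the Intervention description with the Outcome Measures list and the schedule footnote on whether HAM-D depends on the PHQ-9 score.

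The cost is one form revision and a note to interviewers, with no added interview time unless the optional history question is used. The downside is that scores from the old and new wording will not be fully comparable.

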- Hamilton Anxiety Rating Scale: Measures the severity of anxiety through looking at both psychic and somatic anxiety.
- Multidimensional Scale of Perceived Social Support: Scale to determine a patients social support system
- PROMIS: Sleep disturbance scale assess pure domain of sleep disturbance
- Health Care Utilization: Assess ER visits, outpatient visits, rehospitalization and mortality
- Fatigue Severity Scale: Measures the severity of fatigue and its effect on a person's activities and lifestyle in patients exhibiting depression

Participant timeline

The research assistant will administer an approximately 45-minute interview at up to five time points to all patient-subjects: upon enrollment (prior to hospital discharge) as a baseline assessment, and at up to four follow-up visits within 18 months after discharge from the hospital.

The goal will be to do these assessments at the six-week, six-month, and one-year follow-up appointments, taking into consideration that the actual appointments frequently do not occur exactly on the intended timescale. The trial period will be for 12 months after discharge; however, should we need to speak with patients or if they miss their 12 month appointment, we will allow for another timepoint within 18 months.

For patients reaching the end of the study and choosing to discontinue the study drug, the two week weaning period will begin at the completion of the 12-month trial period. Patient education regarding continuation or discontinuation of SSRI treatment at the completion of the study will be provided 90 days prior to reaching the end of the study, regardless of treatment group. From time to time, members of the study team may contact the patient to ensure medication compliance and answer questions about medications and the study the subject may have.

Sample size

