3. SUICIDE

- 0=** Absent
- 1=** Feels life is not worth living
- 2=** Wishes he were dead or any thoughts of possible death to self
- 3=** Suicidal ideas or gesture
- 4=** Attempts at suicide (any serious attempt rates 4)

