
5. Since your last study interview on ____/____/____ did you have an outpatient visit with a psychiatrist, psychologist, social worker, psychiatric nurse, counselor or other similar professional about problems with your emotions or nerves, or use of alcohol?
 
If yes, how many visits did you have with each of the following provider, and what were the visits for?
		Yes (1)	No (0)	Patient Refused (-9)
5a.	Psychiatrist	# visits	What for?	
5b.	General practitioner or family doctor	# visits	What for?	
5c.	Any other medical doctor (GYN, urologist, etc.)	# visits	What for?	

5d.	Psychologist	# visits	What for?	
5e.	Social Worker	# visits	What for?	
5f.	Counselor	# visits	What for?	
5g.	Any kind of substance abuse or chemical dependency treatment, like AA, NA a sobering center, or detox	# visits	What for?	
5h.	Any other mental health professional	# visits	What for?	
5i.	Nurse, occupational therapist, or other health profession	# visits	What for?	
5j.	Religious or spiritual advisor like a minister, rabbi, or priest	# visits	What for?	
5k.	Any other healer, like an herbalist, chiropractor, or spiritualist	# visits	What for?	

	How many times since your last study interview on ____ / ____ / ____ , have you been a patient over night or longer in a hospital for any reason?		
6a.	_____ # times		
	If you can recall the first hospitalization since ____ / ____ / ____ , can you tell me:		
6b.	[6b1.]	Where you were seen:	
	[6b2.]	What your primary complaint was:	
	[6b3.]	How many days you were in the hospital:	
	[6b4.]	Was this related to your original injury hospitalization?	
	If you can recall the second hospitalization, can you tell me:		
6c.	[6c1.]	Where you were seen:	
	[6c2.]	What your primary complaint was:	
	[6c3.]	How many days you were in the hospital:	
	[6c4.]	Was this related to your original injury hospitalization?	
	If you can recall the third hospitalization, can you tell me:		
6d.	[6d1.]	Where you were seen:	
	[6d2.]	What your primary complaint was:	

	[6d3.]	How many days you were in the hospital:	
	[6d4.]	Was this related to your original injury hospitalization?	

	Since your last study interview on ____/____/____, how many visits did you make to an emergency room?		
7a.	_____ # visits		
	If you can recall the first visit since ____/____/____, can you tell me:		
7b.	[7b1.]	What was the visit for?	
	[7b2.]	Where were you seen?	
	If you can recall the second visit, can you tell me:		
7c.	[7c1.]	What was the visit for?	

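### PHQ-9 item 9b, the form's only attempt question, is skipped when there is no current plan and looks back only two weeks, so attempts between visits are captured incompletely

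*Combined protocol and SAP*

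**What the plan says.** The PHQ-9 form puts two unscored Yes/No questions under item 9 (thoughts of death or self-harm). The first is "9a.] Do you currently have plans to harm yourself or take your own life? Yes No if no, proceed to next section". The second, reached only after a yes, is "Have you attempted to carry out this plan in the past two weeks". No other question on that form concerns an attempt. Item 9 also carries a note: "if any endorsement, RA assess further and contact PI".

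The Participant timeline section sets the visits: "The goal will be to do these assessments at the six-week, six-month, and one-year follow-up appointments". A further contact is allowed up to 18 months.

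Other parts of the plan can also pick up an attempt:

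- **HAM-D item 3 (Suicide)** gives its top score to an attempt. The footnote to the schedule table restricts the HAM-D to patients whose PHQ-9 total is above 4. The Intervention description section says that every measure is taken at every time point.
- **The Self-Report Health Service Utilization form** asks about outpatient mental-health visits (item 5), hospital stays (item 6) and emergency visits (item 7). Each is framed "Since your last study interview on" and includes the reason.
- **The interviews** ask about drug side effects (Intervention description).
- **Adverse event reporting and harms** requires possibly related serious events to be reported within 7 days of the team learning of them.

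**The concern.** The skip depends on the wrong fact. Whether a patient has a plan today says little about whether an attempt was made since the last visit. A patient who made an attempt ten days ago and has no plan now goes to the next section without being asked. An unplanned attempt fits 9b poorly even when it is reached, because 9b refers back to the plan just named. The two-week recall also does not match visits that are weeks to months apart, although the health-use form in the same booklet already covers the whole interval.

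At stake is whether the trial learns of an attempt at all. The investigator's reporting and the independent medical monitor's reviews, at least every 6 months, can act only on events that reach them.

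**Working it through.** The plan gives no figure to reproduce. The check compares the recall window with the visit schedule, then looks at the other routes.

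**Inputs.** The recall window is 14 days (PHQ-9 form, 9b). Visits are at six weeks, six months and one year (Participant timeline), taken as days 42, 183 and 365 after discharge. Best case for the form: three visits on schedule, and 9b always asked.

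**Formula.** Share of days inside the window = 14 / (days since the previous visit).

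| Interval | Days | Share inside 9b's window |
|---|---|---|
| Discharge to six weeks | 42 | 14/42 = 33% |
| Six weeks to six months | 183 − 42 = 141 | 14/141 = 10% |
| Six months to one year | 365 − 183 = 182 | 14/182 = 8% |
| Whole year | 365 | 3 × 14 = 42; 42/365 = 11.5% |

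So 365 − 42 = 323 days (88.5%) lie outside the window.

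**Late visit.** With a fourth visit at 18 months (about day 548), the share is 56/548 = 10.2%. If the one-year visit is missed and made up at 18 months, it is 42/548 = 7.7%.

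**From time to attempts.** This step needs an assumption that the documents do not supply. Suppose attempts are spread evenly within each interval, a share f falls in the first six weeks, and 9b is always asked. The share inside the window is then f × 14/42 + (1 − f) × 28/323. This gives 11.5% at f = 11.5%, 21.0% at f = 50% and 33.3% at f = 100%. Attempts clustered just before visits would give more; the skip after 9a would give less.

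**Other routes.**

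| Route | What it adds | Where it stops |
|---|---|---|
| Note to item 9 | Applies to any endorsement, whatever the answer to 9a | No set question, recall period or data field; needs item 9 to be endorsed |
| HAM-D item 3 | Rates attempts, with no plan condition | No recall period printed; under the footnote, only if PHQ-9 exceeds 4 |
| Side-effect questions | Asked at interviews | No question on attempts is specified |
| Health-use items 5 to 7 | Cover the whole interval | Only if the attempt led to care and is named as the reason |

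On the HAM-D condition: item 9 scores at most 3, so a patient with 3 on item 9 and 1 elsewhere totals 4, which is not above 4. Under the footnote that patient has no HAM-D.

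**The case against.** The strongest reply is that the form does not stop at 9a. Item 9 looks back: its stem is "Since your injury, how often have you been bothered by any of the following problems". Any endorsement brings in the research assistant and the PI even if 9a is answered no. HAM-D item 3 is a second dedicated suicide item without the plan condition or the two-week limit. Health-use item 5 reaches outpatient mental-health contacts as well as hospital and emergency care. The Sample size section expects about 20 patients and a feasibility result.

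Much of this stands, and it rules out three stronger readings that a reader might infer:

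- **That the trial would miss most attempts, or 88.5% of them.** The percentages are shares of calendar time within one question's window. The documents say nothing about when attempts occur, and the other routes would find some.
- **That a planned safety comparison is biased.** The Statistical methods section specifies no between-arm comparison of suicidality.
- **That the 7-day rule is breached.** That period starts when the team becomes aware of the event, so a gap in the form does not itself break it.

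What the reply does not do is close the gap. The item 9 follow-up is unscripted. Item 9's own time frame is unsettled, because the lead-in to the form speaks of the past month while the stem goes back to the injury. Interviews may also be done by email or mail, where nobody is present to probe beyond the printed skip.

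**Conclusion.** The point holds for PHQ-9 items 9a and 9b. Followed as printed, the form does not ask about an attempt when the patient reports no current plan. When it does ask, its window spans 33%, 10% and 8% of the days in the three intervals, or 11.5% of the year. Those figures are upper limits on time covered. They assume three on-schedule visits and that 9b is asked each time.

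The harm is incomplete capture of attempts for adverse-event reporting and for the medical monitor. Its size in missed attempts cannot be estimated from the documents. Because partial safeguards exist and the remedy is small, this is a cheap improvement rather than a flaw that threatens the trial's conclusions.

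**What to change.** 1. Remove the skip after 9a, so that the attempt question is asked whatever the answers to items 9 and 9a.
2. Drop the reference to the plan. Ask about any attempt since the last study interview, with the interview date filled in as on the health-use form, and record the date of the attempt.
3. At baseline, ask about the time since the injury and record a yes as pre-treatment history, so that it is not logged as an on-study event. At follow-up, assess and report a yes through the process in Adverse event reporting and harms.
4. Reconcile two related inconsistencies. The schedule footnote and the Intervention description differ on who receives the HAM-D. The Intervention description also refers to PHQ-9 suicide items 2 or 3, whereas the form numbers its suicide questions 9, 9a and 9b.

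Items 9a and 9b carry no points, so the PHQ-9 total does not change. Nominal coverage of the year rises from at most 11.5% to 100%, subject to recall and attendance. The cost is a small form edit, a few seconds per interview, and one more sensitive question for patients who report no thoughts or plan.
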